Non-adherence to the heart failure (HF) plan of care after hospital discharge has been associated with clinical outcomes, including the combined endpoint of all-cause mortality and rehospitalization for decompensated HF. Most patients are discharged with a complex set of instructions that include multiple medications (and differing medication administration plans), sodium restricted diet, fluid management actions (daily weight monitoring and in some cases, fluid restriction), monitoring signs and symptoms of HF, activity and exercise, and when to return for follow-up. At discharge, patients (and their families) may not understand that HF is chronic. Improvement in quality of life may be dependent on patients' acceptance of HF as a chronic, irreversible condition that requires self-care monitoring and behaviors (for example, becoming or staying physically active), even when they feel fine. To decrease the complexity of understanding HF, patients receive a HF handbook and a "zones" 1-page handout before discharge. In addition, they can watch multiple video clips of many HF topics and discuss HF self-care with the hospital healthcare team. However, patients may not read (or view) education materials due to health literacy issues, cognitive decline, eyesight issues, fatigue or depression. Patients may rely on lay (family) caregivers to understand self-care expectations and be active partners in care. Caregivers engaged in patients' care may not be present at discharge or may have preconceived or inaccurate ideas about HF self-care after discharge. A recorded message that could be repeatedly played by patients and caregivers might increase adherence to post-discharge self-care behaviors and 7-day follow-up appointments, and have clinical benefits related to a reduction in all-cause mortality and rehospitalization. The purposes of this randomized, controlled study are to examine the effects of use of a novel MyROAD (Recordable On-Demand Audio Discharge) card, given to patients at discharge. The aims of this single-blind, placebo-controlled study are to examine the effects of recorded messages that can be replayed post discharge (delivered via the MyROAD card) on (1) 45-, 90-, and 180-day *first occurrence* and (2) *time to first occurrence* of all-cause and HF-related hospitalization, ED visits and death/ cardiac transplantation/ventricular assist device, (3) 45-day quality of life, symptoms, functional status and perceived adherence to activity recommendations, and (4) 7-day follow-up appointment with the healthcare provider assigned before discharge. A total of 1066 patients (968 + 10% attrition) with decompensated HF will be randomized to either usual care or usual care and receiving a MyROAD card at discharge.

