3. 45-day quality of life, functional status and perceived adherence to activity/exercise recommendations,
4. 7-day follow-up appointment with the healthcare provider assigned before discharge.

Specific aims and hypotheses:

1. Determine the effects of MyROAD on *first occurrence* and *time to first occurrence* of all-cause and HF hospitalization, ED visit, and death (or cardiac transplantation or VAD).

Hypothesis 1a: 45-day post-discharge rehospitalization, ED visit and death will be lower or trend toward lower, and 90- and 180-day first occurrence of hospitalization, ED visit and death will be lower in the MyROAD group compared to the usual care group.

Hypothesis 1b: Time to first event (rehospitalization, ED visit and death) will be longer in the MyROAD group compared to the usual care group at 90- and 180 days.

2. Determine the effects of receiving repetitive HF messages via MyROAD on quality of life, functional status and perceived adherence to activity recommendations.

Hypothesis 2a: Health-related quality of life (specifically, the clinical summary score, quality of life score, total symptom score -and subscales of physical limitations, symptom stability, symptom frequency, and symptom burden- will be higher in the intervention group compared to the usual care group at 45-days, reflecting improved early post-discharge quality of life. [Note: overall summary score (that includes the areas above and also self-efficacy) will be measured but are not included in the endpoint.]

Hypothesis 2b: HF-related symptoms will be less prevalent in number in the MyROAD group compared to the usual care group at 45-days.

Hypothesis 2c: Functional status will be higher in the intervention group compared with the usual care group at 45-days.

Hypothesis 2d: Perceived highest activity/exercise level will be higher in the intervention group compared with the usual care group at 45-days.

3. Determine the effects of receiving repetitive HF messages by MyROAD on adherence to 7-day follow-up appointment after index discharge.

Hypothesis 3: Adherence to 7-day follow up appointment will be higher in the intervention group compared with the usual care group.

METHODS

Design: The study will use a 2-group, randomized, placebo-controlled, single blinded, design. Healthcare providers will be initially blinded to group assignment, but may learn about the card from patient verbalization over time, as it is not possible to blind patients to the intervention, a MyRoad card.

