9. Wheelchair bound, uses a cane or walker, or unable to carry out physical activity, including walking, due to a chronic disability or documented medical condition.

Intervention

MyROAD is a card that has been designed by CC innovators and American Greetings. When the card is opened, there is a general message that is automatically played. Within the card is a heart shaped cutout that has 4 buttons, one in each quadrant. When pressed, each button has audio of one aspect of general HF education: diet, medications, signs and symptoms of worsening condition and physical activity. The buttons can be pressed as desired (for approximately 2 weeks, until the battery expires) to allow playback of messages. At the top of the heart is a space for the phone number of who to call with questions. CCF Marketing and Brand team has been involved in card art and wording including, color choices, formatting, designs and branding/logos. A magnet allows the heart to adhere to metal surfaces as a visual reminder of self-care; see [Appendix A](#). The script was developed by a HF expert clinician ([name]) and reviewed and approved by [name], vice chair of Cardiology and section head of Heart Failure and Cardiac Transplantation in the Heart and Vascular Institute; see [Appendix B](#). The speaker of the script is a professional radio voice (hired by American Greetings). The card material can be written on, as desired by a health care provider; for example, a nurse can write down the specific dietary sodium limit/day or a phone number. The HF discharge instructions are short, global versions of discharge instructions used by Cleveland Clinic and match current global discharge instruction messages on self-care found in our HF Handbook and HF zones sheet, used by all CC hospitals in Northeast OH.

Outcomes and Measurement

Case report forms will be used to collect all-cause and HF hospitalization, ED visit, and death (or cardiac transplantation or VAD) healthcare consumption and also, 7-day adherence to the scheduled post-discharge follow-up appointment.

- Data will be collected at baseline and 45-, 90-, and 180-day days after discharge

Quality of life will be measured using the *Kansas City Cardiomyopathy Questionnaire* (KCCQ). Kansas City Cardiomyopathy Questionnaire (KCCQ) is a 23 item questionnaire that measures

V1_01-20-16

NCT02901314

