- Usual care group patients will be instructed that their healthcare providers (including their nurse caregivers) will deliver usual care discharge instructions and patient education.

7-day follow up appointments are part of usual care. A research nurse will review EMRs of enrolled patients between discharge and 30 days after discharge for adherence to the 7-day follow-up appointment. If not found, at the 45-day telephone call, data will be collected on 7-day follow-up appointment adherence, quality of life, functional status and adherence to activity/exercise recommendations (by short questionnaires) during the telephone call.

45-90 and 180-day healthcare consumption will be assessed in 3 primary ways: EMR review, telephone contact and written paperwork mailed to patient's home (if unable to reach patients by telephone: quality of life, functional status and physical activity/exercise forms-- with a self-

V1_01-20-16

NCT02901314

addressed, pre-stamped envelope for return). In addition, death may be assessed by Social Security Death Index software.

Sample Size

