The main campus of Cleveland Clinic has a high volume of HF discharges each year. Fairview and Hillcrest Hospitals have moderate volumes of HF discharges, and are less likely to have patients who meet exclusion criteria due to enrollment in another research study or advanced HF. Electronic medical records allow for review of data on events that occur in *all* system hospitals and regional medical practice ambulatory care sites; decreasing the need to rely on patient recall of rehospitalization and emergency care events.

The MyCard instructions are a global representation of standard HF discharge instructions found in written handouts and other sources of patient education (videos, verbal instructions from healthcare providers). No new information is presented; thus, the MyRoad card is an extension of usual care delivered in a *different format that is repeatable*. Patients do not need to be able to

read and if they are forgetful, they can replay messages multiple times before the battery cycle ends (around 2 weeks of frequent use).

Nurse managers, clinical nursing directors and cardiologist medical directors of each hospital involved (7th floor J building and general medical units of main campus; multiple medical units of Hillcrest and Fairview Hospital—however, patients with HF are concentrated on PK2-Progressive Care Unit [Fairview Hospital] and 5M [Hillcrest Hospital] are aware that this study will be starting and agreed (and were actually excited) that we are included their patients/units. Research personnel from the Office of Nursing Research and Innovation will be involved in recruitment and all data collection. The main campus has multiple research projects in place. My team is accustomed to working with cardiology research nurses to ensure patients are not approached for more than 1 research study.

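### The trial is labelled placebo-controlled and single-blind, but controls get usual care with no sham card, patients are unblinded and no masking of outcome collectors is described, so the 45-day self-reports lack the protection the label implies

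*Combined protocol and SAP*

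**What the plan says.** The label appears twice. The opening summary speaks of "The aims of this single-blind, placebo-controlled study", and the Design paragraph under Methods says "The study will use a 2-group, randomized, placebo-controlled, single blinded, design".

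The arms are described differently. In the summary, patients "will be randomized to either usual care or usual care and receiving a MyROAD card at discharge". Under Data Collection the control arm gets information only: "Usual care group patients will be instructed that their healthcare providers" will give the usual instructions and education. No dummy or silent card is mentioned anywhere.

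On blinding, the sentence after the label in the Design paragraph says that providers are blinded at first and may later learn of the card from patients, and that patients cannot be blinded. The Intervention section allows providers to write on the card; for example, "a nurse can write down the specific dietary sodium limit/day or a phone number". Data Collection allows the card to be handed over at enrolment, while the patient is still in hospital.

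On outcome collection, the Feasibility section says that research personnel from one office "will be involved in recruitment and all data collection". Data Collection has research personnel hand out the card. For the 7-day visit the record is searched first: "If not found, at the 45-day telephone call, data will be collected on 7-day follow-up appointment adherence". The Limitations section does not mention reporting or ascertainment bias.

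**The concern.** A placebo control and blinding protect outcomes that depend on what patients expect or on how they are questioned. The 45-day outcomes under Aim 2 are of that kind: KCCQ, the symptom checklist, DASI and the one-item activity tool all come from the patient, by telephone or mailed form. Patients in the card arm know that they were given something extra.

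The card also speaks to what is measured. The Appendix B script encourages regular walking and attendance at scheduled visits. The activity item asks for the highest level of purposeful walking, and Aim 3 counts visit attendance.

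If the label is carried into a report, readers will credit the Aim 2 and Aim 3 results with a protection that the design does not provide.

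**Working it through.** **Step 1: label against description.**

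| Property implied by the label | What the protocol describes | Section |
|---|---|---|
| Placebo control | Usual care alone; no sham card | Summary; Data Collection |
| Patients blinded | Stated to be impossible | Design |
| Providers blinded | Only at first; may learn from patients; may write on the card | Design; Intervention |
| Interviewers, record reviewers, event classifiers masked | Not addressed; one office recruits and collects all data | Feasibility |

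The first row contradicts the label. The second and third rows leave a narrow sense in which single-blind is true, but the blinded party, the provider, does not supply the Aim 2 outcomes. The fourth row is a gap in the text.

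**Step 2: which outcomes are exposed.** KCCQ, symptoms, DASI and activity are fully patient-reported. The 7-day visit is exposed only where no visit is found in the record and the answer comes from the call. Hospitalizations and emergency visits found in the record, and deaths, are much less exposed. Calling an event heart-failure related involves judgement, and the protocol does not say who makes that call or what they know.

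**Step 3: illustration of size.** The plan has no figure to reproduce here: it gives no KCCQ standard deviation and names no test for Aim 2. Inputs:

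- Sample sizes from the Sample Size section: minimum 281 per group, full 533 per group.
- Loss of 10%, an assumption for day 45 that borrows the plan's 30-day allowance: 281 × 0.9 ≈ 253 and 533 × 0.9 ≈ 480 analysed per group.
- SD of 20 to 25 points (assumption).
- No true effect; a differential reporting shift b of 1, 2 or 3 points (assumption). For scale, the protocol cites 5 points on the clinical summary score as matching one NYHA class.
- Comparison of two means at two-sided 0.05 (assumption).

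SE = SD × √(2/n). The probability of a significant result favouring the card is P(Z > 1.96 − b/SE). It is 2.5% when b = 0.

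Example: SD 20, n = 253 gives SE = 20 × √(2/253) = 1.78. With b = 2, 1.96 − 2/1.78 = 0.84, so the probability is about 0.20.

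| n per group | SD | b = 1 | b = 2 | b = 3 |
|---|---|---|---|---|
| 253 | 20 | 0.081 | 0.202 | 0.392 |
| 253 | 25 | 0.066 | 0.144 | 0.271 |
| 480 | 20 | 0.118 | 0.340 | 0.642 |
| 480 | 25 | 0.090 | 0.235 | 0.460 |

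The range is about 7–39% at the minimum size and 9–64% at the full size. With no loss at all it is 7–43% and 10–69%, so the loss assumption matters little. The probability rises with sample size because a fixed bias does not shrink while the standard error does.

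For the 7-day visit, a spurious difference would equal the share of patients with no recorded visit times the between-arm difference in over-reporting. The documents give neither, so no figure is put on it.

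**The case against.** Several points on the other side stand.

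- **Masking of collectors.** A reader might infer that interviewers and record reviewers are unmasked. The protocol does not say so. That one office recruits and collects data does not mean that the person who gave the card makes the call or holds the allocation. The text supports only that no masking is described.
- **Disclosure.** A reader might infer that single-blind is empty or misleading. The next sentence of the Design paragraph says who is blinded and for how long, and admits that patients are not. Writing on the card makes provider blinding fragile, as the word initially already signals; it does not show that blinding was never there. For the same reason, open-label would be an inexact replacement.
- **The 7-day visit.** The record already comes first, and the Feasibility section says it covers all system hospitals and regional ambulatory sites. The messages are described as standard care with no new information, so their content alone does not separate the arms. Replay and awareness of allocation still could. A record-only main analysis would lose genuine visits outside the system, and nothing in the documents shows that this loss would be equal between arms.
- **Reach.** The first comparison in the Analyses section, death or at least one readmission by 6 months, rests largely on records. A usual-care comparison with unblinded patients is a legitimate design.
- **Size.** The SD and the bias are assumed; the documents supply neither.

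These points narrow the concern. They do not rescue the term placebo-controlled, and they do not give the self-reported outcomes any blinding.

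**Conclusion.** The concern holds in a limited form. Placebo-controlled is wrong on the protocol's own description. Single-blind is true only of providers and only at the start, and it protects none of the patient-reported Aim 2 outcomes. The protocol is silent on masking of those who collect or classify outcomes, and it does not list self-report bias among its limitations.

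The consequence is confined to the 45-day self-reports, 7-day visits taken from the call, and events whose classification involves judgement. The documents do not support reading this as a threat of the same order to death or record-captured hospitalization, or as concealment.

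The false-positive ranges in the working show that a shift well under the cited 5 points could matter. They are illustrations that depend on the assumed SD and bias, not estimates of the bias in this trial.

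**What to change.** 1. In the opening summary and the Design paragraph, describe the trial as randomized and usual-care-controlled, with patients unblinded and providers initially unaware of allocation. State for interviewers, record reviewers and event classifiers whether each is masked.
2. Limit the conclusions for Aims 2 and 3 to match, and add self-report bias to the Limitations section.
3. Within the existing team, assign the 45-day calls and the classification of events as heart-failure related to members who did not enrol the patient and do not hold the allocation.
4. Keep the record-first rule for the 7-day visit, and add a sensitivity analysis that counts only visits documented in the record.

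The cost is wording, one extra analysis and some scheduling of tasks; no added staff should be needed. The gain is partial: masked callers reduce interviewer effects but not patient expectation, patients may reveal their arm during the call, and self-completed or mailed forms have little interviewer effect to remove. That residual is why the second item is needed alongside the third.

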Based on historical readmission rates among subjects receiving the current standard of care treatment (~ 20% and dropping slightly every year), a 30-day readmission rate of 18% is expected. We are also basing the sample size on an expected 90-day rehospitalization rate of 25% and a 180-day rehospitalization rate of 35%; both of which are conservative. Sample size calculations were performed to show minimum sample size needed to detect a decrease of 30% at 30-days, 90-days and 180-days with the addition of the card. In many research studies, trends toward improvement are found at 30 days, but the trend is not significant till further out (90 days or 180 days). Thus, we are hypothesizing that a trend will be seen at 30 days, but that there will be significant differences at 90 days and 6-months. A total sample size of 968, 734 and 468 are needed to achieve 80% power in 30-day, 90-day and 180-day rehospitalization rates, respectively. These calculations assumed a balanced randomization and use of one-sided Pearson chi-square tests with a significance level of 0.05. Calculations were performed using SAS software (version 9.2; Cary, NC). To account for attrition in follow-up, sample size was increased by 10-% at 30-days and 20% at 90- and 180-days, creating ideal sample sizes of 1066 (533 per group; to achieve power at 30-days), 882 (441 per group; to achieve power at 90-days) and 562 (281 per group; to achieve power at 180-days).

- Thus, our *minimum sample size* will be 562 subjects. If trends in outcomes are favorable, data collection will continue to reach the required sample size for 90-day outcomes.

Analyses

Patient characteristics will be summarized using frequencies and percentages for categorical factors, and means, standard deviations, and percentiles of interest for continuous measures. Pearson chi-square tests will be used to compare the proportion of subjects meeting the composite endpoint of death or at least 1 readmission by 6 months. Secondary analyses will use Poisson regression to compare readmission rates (number of readmissions/follow-up days), and competing risk survival methods will be used to compare time to first readmission between groups. Analyses will be performed assuming a 0.05 significance level. Analyses will be performed using SAS software (version 9.2 or higher; Cary, NC).

Feasibility

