Self- or research nurse-administered instruments that will be completed at baseline, 45, 90 and 180-days are short, simple and will be quick to complete. Patients may become fatigued when completing data collection forms; however, there are only 5 forms for patients to complete at baseline (quality of life, symptoms, functional status, physical activity/exercise and a case report form of demographic information); all of which are short (most are single page) and should not take more than 10 minutes to complete. The 4 forms used at 45 days should take no more than 5 minutes to complete. We have used all instruments in previous research and do not anticipate a burden to patients who enroll. There is only a telephone call at 90- and 180-days. Data obtained from electronic medical records is consistently present, minimizing the occurrence of missing data.

Limitations and Anticipated Problems

Patients and caregivers may never listen to the recorded message after discharge, or loose, throw out or misplace the card. Patients may hear, but ignore, message content. Patients may drop out before the 180-day follow-up data collection. Patients in both groups may ignore self-monitoring and self-care messages based on past practices, implicit beliefs about how to monitor and care for self or misperceptions of family or friends. Analyses will be completed using “intent to treat” methods. In this way, we will be able to learn the effect size of the intervention among all patients randomized to the intervention group.

No adverse effects are anticipated, as the intervention in this research is a greeting-type card that cannot create harm to patients. The audio script provides global messages of content used in usual care education and discharge instruction materials. There are no risks of adverse events from the intervention itself.

Human Subjects Protection

Approval by the Cleveland Clinic Institutional Review Board will be sought prior to study initiation. We believe this study is minimal risk as the intervention is a greeting-type card that repeats self-care monitoring and instruction messages that are part of usual heart failure post-discharge care.

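### A 7-day visit not found in the record is settled only by the day-45 call, the listed mailing omits the question, and no rule says how unresolved patients count for Hypothesis 3

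*Combined protocol and SAP*

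**What the plan says.** The third specific aim is stated as "Hypothesis 3: Adherence to 7-day follow up appointment will be higher in the intervention group compared with the usual care group".

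Data Collection gives two sources, used in sequence. The first is the record: "A research nurse will review EMRs of enrolled patients between discharge and 30 days after discharge for adherence to the 7-day follow-up appointment". The second applies only when the first fails: "If not found, at the 45-day telephone call, data will be collected on 7-day follow-up appointment adherence".

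The same section describes paperwork to be posted with a return envelope, "if unable to reach patients by telephone: quality of life, functional status and physical activity/exercise forms". No appointment item is in that list.

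Outcomes and Measurement places on case report forms the healthcare-use events and "also, 7-day adherence to the scheduled post-discharge follow-up appointment", with collection at baseline and at 45, 90 and 180 days. It does not say that an appointment question missed at day 45 is asked later.

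Feasibility describes the record as covering "system hospitals and regional medical practice ambulatory care sites", so a visit elsewhere may not appear.

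Analyses does not mention this endpoint. Limitations and Anticipated Problems says "Analyses will be completed using “intent to treat” methods", with no scoring or imputation rule.

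**The concern.** The two sources do not carry the same risk of loss. A patient whose visit is in the EMR has a value whatever happens later. A patient with no visit found has one only if the day-45 call is completed. Values are therefore lost mainly on the side where attendance is lower. This happens even if every telephone answer is true, so it is separate from inaccurate recall.

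With no stated rule, the analyst must choose after the data are in between dropping unresolved patients and counting them as not adherent. Dropping them overstates adherence in each arm. It also favours whichever arm is harder to reach by telephone, so the bias could run for or against the card. Design states that patients cannot be blinded to the card, and the plan does not say that callers are blinded, so unequal reach is possible.

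**Working it through.** The plan gives no expected rate, power or test for Hypothesis 3, so there is no planned figure to reproduce. The check is algebra on the scoring rule.

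**Inputs**
- q, share of patients with a visit found in the EMR: 40–60%. Assumption; the documents give no rate.
- r, share of not-found patients who kept a visit elsewhere: 0 or 20%. Assumption.
- u, share of not-found patients not reached: 10–20%. Assumption, guided by Sample Size, where "sample size was increased by 10-% at 30-days and 20% at 90- and 180-days". Those are planning allowances at other time points, not call non-contact.
- 533 per arm (N=1066), or 281 per arm at the stated minimum of 562.

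**Formulas, if unresolved patients are left out**
- Unscored share = (1−q)u
- True rate = q + (1−q)r
- Scored-only rate = [q + (1−q)(1−u)r] / [q + (1−q)(1−u)]

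**Each arm**

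| q | r | True | Scored-only, u=10% | Scored-only, u=20% |
|---|---|---|---|---|
| 40% | 0 | 40.0% | 42.6% | 45.5% |
| 40% | 20% | 52.0% | 54.0% | 56.4% |
| 50% | 0 | 50.0% | 52.6% | 55.6% |
| 50% | 20% | 60.0% | 62.1% | 64.4% |
| 60% | 0 | 60.0% | 62.5% | 65.2% |
| 60% | 20% | 68.0% | 70.0% | 72.2% |

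For example, q=50%, r=0, u=20% gives 0.5/(0.5+0.5×0.8) = 55.6%. The unscored share runs from 0.4×0.1 = 4% to 0.6×0.2 = 12%. The overstatement runs from 2.0 to 5.6 points.

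**Equal reach in both arms.** With no true effect the scored-only rates are identical and the test keeps its 5% level. With a true 50% versus 60%, r=0 and u=20% in both arms, the scored-only rates are 55.6% and 65.2%. The difference is 9.7 points instead of 10.0, and the odds ratio stays at 1.50.

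**Unequal reach, no true effect (20% non-contact in the card arm, 10% in usual care).** Take q=50%, r=0.
- False difference: 55.6% − 52.6% = 2.9 points before rounding.
- Scored patients: 533×0.90 ≈ 480 and 533×0.95 ≈ 506.
- SE = √(0.556×0.444/480 + 0.526×0.474/506) ≈ 3.2 points, so the shift is 0.92 SE.
- Rejection at nominal 5%: one-sided P(Z > 1.645−0.92) ≈ 23%; two-sided ≈ 15%.

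Across the six q and r combinations, the false difference is 2.2–2.9 points, with one-sided rejection of 18–23% and two-sided 11–15%. If card patients are the easier to reach, one-sided rejection in favour of the card falls below 1%.

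At 281 per arm the false difference is the same but the SE is larger (4.4 points in the example). Rejection is then about 13–16% one-sided and 8–10% two-sided.

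**Counting the unresolved as not adherent.** The rate becomes q + (1−q)(1−u)r. With q=50% and r=20%, this gives 59% at u=10% and 58% at u=20%, against a true 60%. Unequal reach then leaves 1.0 point of bias against the harder-to-reach arm, compared with 2.3 points in its favour if those patients are dropped. The two biases are equal in size when r is about 37%.

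**The case against.** A reader might infer that every patient without a value is a non-attender, that such patients will be dropped, and that the test of Hypothesis 3 is therefore compromised. The documents do not support that reading, for five reasons.

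- **What counts as found.** The nurse reviews the record for adherence. A recorded no-show or cancellation could count as a finding, which would score some non-attenders without a call and weaken the link between outcome and loss.
- **The mailed list may be incomplete.** The paperwork is offered as a way to assess healthcare use, yet no healthcare-use form is listed. The symptom form is also absent, although symptoms are collected at 45 days.
- **Later capture is possible.** Outcomes and Measurement gives 90- and 180-day collection times, and participation involves three calls.
- **Exclusion is not stated.** Intent-to-treat wording is compatible with counting the unresolved as not adherent.
- **The arm gap is assumed.** The 10% and 20% are attrition allowances at different times, not observations in different arms. The one-sided test is specified only for the rehospitalisation sample size; sidedness for Hypothesis 3 is unstated.

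All five stand as limits on the strength of the claim. None supplies the missing rule. No text clearly puts the question to a patient missed at day 45, and none says how that patient counts.

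**Conclusion.** The concern holds in a limited form. Appointment status depends on a completed day-45 call when no visit is found, the mailed fallback as listed does not cover it, and the plan has no rule for those left over. They come mainly, not necessarily entirely, from patients with no recorded visit.

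Leaving them out would overstate adherence by about 2 to 5.6 points per arm under the assumed ranges. It would distort the arm comparison only if reach or EMR capture differs by arm. The false difference of 2.2–2.9 points illustrates a 10% versus 20% gap and is not a prediction; a smaller gap gives less, and equal reach leaves the test essentially intact. This is one of several aims, and the point should be settled before analysis because the remedy is cheap.

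**What to change.** 1. Add one appointment question to the paperwork already mailed to patients not reached by telephone, and ask it at the 90-day call if status is still unresolved.
2. In Data Collection and Analyses, define Hypothesis 3 for all randomised patients discharged home. Count a visit within 7 days as kept if it is found in the EMR or reported by telephone or on the mailed form, and a recorded no-show as not kept. State also how a patient who dies or is readmitted before day 7 counts.
3. Count patients still unresolved as not adherent in the main comparison. Add a sensitivity analysis that multiply imputes their status from the resolved not-found patients in the same arm.
4. Report, by arm, the source of each score and the number unresolved.

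The cost is a few sentences of plan text, one line on an existing form and one question at an existing call. The downside is that reported adherence will be a few points lower than a scored-only figure, and visits kept outside the system by unresolved patients will be misclassified. That leaves about 1 point of arm bias if half are found in the EMR, 20% of the rest attended elsewhere, and non-contact is 10% versus 20%. The imputation analysis would show its size.
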